Assessment of PA behaviors were collected at two timepoints each year – during school (April/May, average daylight 13hrs) and again during summer (mid-July, average daylight 14hrs). Children were instructed to wear the device during school and summer for 14 consecutive days during each assessment period. Devices were distributed and returned by mail. Each mailing contained a device and information regarding wear procedures (e.g., wear while awake and sleeping, waterproof). Data were downloaded and saved in raw format as .gt3x files and were processed using the GGIR package (version 2.8-2) in R (Version 4.1.2; R Foundation for Statistical Computing; Vienna, Austria). Time spent in PA intensity categories was determined using intensity thresholds described by Hildebrand et al.^{3,4} A valid wear day was defined as a minimum of 16 hours and participants were included if they had at least one day of data.⁵ The primary metrics of interest were time spent in MPVA and time spent sedentary in minutes per day.

Sleep. The amount of time (minutes per day) a child sleeps was collected via the wrist-placed ActiGraph on the non-dominant hand (described above).⁶⁻⁸ This procedure has been validated as a measure of sleep and is used extensively in studies evaluating sleep.⁷⁻¹¹ The amount of time a child sleeps each night will was determined using two methods that are widely used in the sleep literature with children: 1) ActiGraph proprietary sleep algorithms to determine time spent sleeping, and 2) cross-referencing with parental/guardian report of time in bed and time of wake from the daily logbook.

Screen Time. Each evening of the 14-day accelerometer protocol, parents received a text via their smartphone to complete a time use record (see “Structured Program Exposure – Time Use Record” section below for details). One of the questions of the time use record asked parents to estimate the total amount of time (hours and minutes) their child spent in front of a screen that day (e.g., TV, computer, video game, smartphone, and tablet).

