MVPA, Screen Time, Sleep. The primary analysis was intent-to-treat (ITT), defined as using all available data from children according to the original group they were randomized (free summer day camp or summer as usual) regardless of their attendance at a summer program (e.g., intervention children never attending the SDC and control children attending some other form of SDC). Analyses used mixed-effects models, accounting for the nesting of repeated measures within children, families, and schools. The treatment effect of interest was the group (intervention vs control) and time (pre summer vs post summer) interaction. Missing data on the dependent variables of interest of MVPA, time spent sedentary, sleep, and screen time were accounted for using full information maximum likelihood estimation,²⁵ allowing for all children's data to be used regardless of missing data at either pre or post summer. Covariates included in the model were the child's biological sex¹⁹ and age,²⁰ self-reported race/ethnicity,²¹ parent education,²² food insecurity status,²³ and poverty level.²⁴ Missing data on covariates were handled using multivariate multiple imputation with the covariates serving as variables to inform the imputation of 100 datasets for both continuous and categorical covariates using STATA v18.0 multiple imputation commands.

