Secondary analyses (i.e., exposure models) examined the exposure to structured programming and included both the intervention and control groups. For these analyses we defined exposure to structure as any day where a child is reported on the TUR to have attended a structured setting outside the home (attended/not attend, binary variable). This choice of dichotomizing structured settings at the day level was done because the distribution of minutes in a structured setting was heavily skewed in the summer. Children (both intervention and control), when they were reported to have attended a structured setting in the summer, did so for a day-long program (i.e., 7-8hrs), which for the intervention group was the typical length of attending the SDC. This means that for the children in the control group, when they did attend structured programming in the summer, this programming lasted for approximately the same length of time as the intervention group. Because all children were exposed to school, exposure to structured programming during school (April/May) excluded attending school and, therefore, represents only additional structured programming a child was exposed to above and beyond the school day. In addition to changes in the continuous outcomes, we examined the probability of meeting MVPA (≥ 60 minutes per day) and screen time (≤ 120 minutes per day) guidelines²⁶ using both the above stated ITT and exposure to structured programming models. All models included both weekdays and weekend days. Because free SDC was provided on weekdays only, we also conducted the same ITT and exposure analysis restricting the data to only weekdays. The assumptions for all models (normality of residuals, homoscedasticity) were checked using; no violations were found. All models were conducted using STATA v18.0 (College Station, Texas).

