Diet. The primary analysis was intent-to-treat (ITT), defined as using all available data from children according to the original group they were randomized to (free SDC or summer as usual) regardless of their parent-reported attendance at a summer program.²⁷ Mixed effects models were used to account for the nesting of repeated daily measures within children. The analyses examined the odds of consuming different foods/beverages during weekdays in the summer, controlling for school year endorsement of consuming that food or beverage, in the free SDC group compared to summer as usual. During analysis, day-level food/beverage response options (e.g., 1 time today, 2-3 times today) were collapsed and recoded as binary values: 1 = consumed and 0 = did not consume. Analyses excluded weekend days as the intervention was only delivered on weekdays. Missing data for outcome variables were accounted for using full information maximum likelihood estimation, allowing for all children's data to be used regardless of missing data. Covariates included child biological sex, parent education, food security status, the use of assistance services (e.g., SNAP, WIC), and income. Missing data for covariates was handled using multiple imputation of 100 datasets for both continuous and categorical covariates.

Secondary analyses were as-treated, defined as using all available data from children based on their parent-reported attendance at a structured program on weekdays in the summer, regardless of what group they were randomly assigned to.²⁸ This analysis examined the impact of attending structured summer programming, both

as a binary predictor (days children attended vs days not attended) and as categorical minutes attended (30-239min/d or ≥ 240 min/d vs did not attend “zero” minutes [reference group]) on the odds of consuming different food/beverages during weekdays in the summer, controlling for consumption during the school year and all covariates included in the primary analysis. The 30-239min/d grouping corresponds to half-day or shorter programs, while ≥ 240 min/d corresponds to longer than half-day up to full-day programs. The assumptions for all models were evaluated by examining multicollinearity, residual plots, and the distribution of random effects; no violations were found. STATAv17.0 was used to run all statistical analyses

References

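### If the MVPA, sedentary, sleep and screen-time models use daily rows, as the text implies, their stated random effects omit child-by-season variation and the group-by-time standard errors are too small

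*Combined protocol and SAP*

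**What the plan says.** The relevant text is in the combined protocol and SAP, under Measures and under Statistical Analyses (the MVPA, Screen Time, Sleep paragraphs).

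- **Model levels:** "Analyses used mixed-effects models, accounting for the nesting of repeated measures within children, families, and schools".
- **Tested effect:** "The treatment effect of interest was the group (intervention vs control) and time (pre summer vs post summer) interaction".
- **Data per child:** "Children were instructed to wear the device during school and summer for 14 consecutive days during each assessment period". Screen time comes from an evening parent report over the same 14 days. A child is included with as little as one valid wear day.
- **Row unit:** not stated. Three sentences bear on it. "All models included both weekdays and weekend days". Because the camp ran on weekdays, "we also conducted the same ITT and exposure analysis restricting the data to only weekdays". The explanation of the exposure variable begins "This choice of dichotomizing structured settings at the day level".
- **Guideline outcomes:** the probability of reaching at least 60 minutes of MVPA per day, and of at most 120 minutes of screen time per day, is modelled with the same ITT and exposure models.
- **Not mentioned:** a child-by-season effect, a random slope for time, a residual correlation structure or a robust variance. The assumption checks named are normality of residuals and homoscedasticity, not independence.
- **Comparison with diet:** the diet analysis describes daily measures within children and models summer weekdays only, "controlling for school year endorsement of consuming that food or beverage".

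**The concern.** Group by time compares the arms on each child's summer-minus-spring shift. For a child seen in both seasons, the child, family and school intercepts cancel from that shift. The model's standard error for the interaction therefore rests on the residual alone, and with daily rows the residual is mostly day-to-day noise.

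Children should differ in their shift. Spring is a shared school setting, while summer differs from child to child. The plan itself expects about 20% of controls to attend a program, and it allows for intervention children who never attend. Siblings are allocated together, so any shift they share adds to the problem. More wear days reduce the day noise but not this variation, yet the stated model treats both as shrinking together. Extra days then count almost as extra children.

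At stake are the intervals and p-values for four continuous behaviours, two guideline outcomes and their weekday-only reruns. These results would be used to explain how the camp works. The nesting sentence closely matches the one for zBMI, where each child has two values and a child intercept is enough.

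**Working it through.** The plan gives no variance, valid-day count or power figure for these outcomes, so there is no plan figure to reproduce. Its sample-size calculation concerns zBMI only.

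**Inputs from the documents**
- Levels: child, family, school. Effect: group by time.
- Days per season, m: at most 14 (10 if weekdays only), at least 1.
- Alpha 0.05 (stated for zBMI; taken as two-sided). Final sample 330, or 165 per arm (used only in the simulations).

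**Assumptions, not in the documents**
- Balanced daily rows, both seasons observed, no family or school variance.
- Total variance 1, child ICC 0.35, child-by-season variance s of 0.03, 0.05 or 0.10, day variance e = 0.65 - s.

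**Step 1. True variance.** A child's difference in season means has variance 2(s + e/m) = (2/m)(ms + e).

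**Step 2. Variance the model uses.** With only a child intercept, the residual pools day noise and the child's shift over 2m - 1 degrees of freedom per child. Its expectation is e + s·m/(2m - 1), so the model assigns (2/m)[e + s·m/(2m - 1)].

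**Step 3. Ratio.** With rho = s/(s + e):

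R = [m·rho + (1 - rho)] / [(1 - rho) + rho·m/(2m - 1)]

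Type I error = 2[1 - Phi(1.96/√R)]. The standard error is too small by 1 - 1/√R. R does not depend on the number of children.

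**Step 4. Two cases in full**
- s = 0.03, m = 5: rho = 0.03/0.65 = 0.046. R = 1.185/0.979 = 1.21, √R = 1.10, 1.96/1.10 = 1.78. Type I error 7.5%; SE 9% too small.
- s = 0.10, m = 10: rho = 0.10/0.65 = 0.154. R = 2.385/0.927 = 2.57, √R = 1.60, 1.96/1.60 = 1.22. Type I error 22.2%; SE 38% too small.

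**Step 5. Type I error over the assumed range**

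| Days per season | s = 0.03 | s = 0.05 | s = 0.10 |
|---|---|---|---|
| 5 | 7.5% | 9.2% | 13.7% |
| 10 | 10.3% | 13.9% | 22.2% |
| 14 | 12.5% | 17.4% | 27.6% |

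A simulation of 4,000 replicates under the same assumptions gave 7.6% (s = 0.03, 5 days) to 23.6% (s = 0.10, 10 days), with SEs 9-39% too small.

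**Step 6. Sensitivity.** By the formula, type I error is 6.0% at m = 5 with rho = 0.02, 8.2% at m = 14 with rho = 0.02, and 32.6% at m = 14 with rho = 0.20. At rho = 0 or m = 1, R = 1 and the error is 5%.

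**Step 7. Checks.** Simulations with 330 children and 2,000 runs per cell agreed with the formula: at m = 14, 8.5% for rho 0.02 and 19.7% for rho 0.10 (formula 8.2% and 20.7%). A run of 400 mixed-model fits at m = 10, rho = 0.10 rejected 15.3% (formula 16.5%). Testing child-level change, which is equivalent to adding the child-by-season component, gave 4.5-5.5% in every cell.

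**Step 8. Spring adjustment.** If the season means correlate at r, adjusting for the spring mean instead of analysing change cuts the variance by (1 - r)/2. Here r = 0.35/(0.35 + s + e/m). Over the 5- and 10-day cells r runs from 0.63 to 0.79, a saving of about 10-19%. This is precision only.

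**The case against.** **Row unit.** The main models are never said to use daily rows. Missingness is described by occasion, before or after summer, which reads like two values per child. The diet paragraph says daily when it means daily, and the day-level coding is stated for the secondary exposure models. Season means recomputed over different sets of days would also fit the text. This stands in part: daily rows are an inference. They remain the natural reading, because all models are said to contain both kinds of day, the ITT models are rerun on weekdays, and the guideline outcomes are per-day thresholds.

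**Unreported structure.** A random time slope or child-clustered errors may have been used and not reported. Either would remove or largely reduce the problem. This stands, but the model as written has neither.

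**Limits of the calculation.** The variances are assumed, and the set-up is balanced with continuous outcomes and no family or school variance. The effect of siblings' shared shift and the inflation in the binary guideline models are not quantified. For children seen in one season only, the child intercept does not cancel. All of this stands.

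**Stronger readings that the documents do not support**
- A reader might infer that this trial's type I error is known to be 8-24%. No document figure supports that. The value could be close to 5% or above 30%.
- A reader might infer that spring behaviour is ignored because it is not a covariate. Spring days are outcome rows, so group by time already removes each child's spring level. What is lost is precision; no bias follows.
- A reader might infer that the primary result is affected. zBMI has one value per occasion, so the argument does not reach it.

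**Conclusion.** The concern holds conditionally. If rows are days, the stated levels leave child-by-season and sibling-shared season variation out of the group-by-time standard error. The direction is then certain: whenever that variation is above zero and children have more than one day per season, intervals are too narrow and type I error exceeds 5%. The size is illustrative: about 7.5% to 22-24%, with standard errors 9-39% too small, for a child ICC of 0.35, a child-by-season share of 3-10% and 5-10 valid days per season. If rows are season means, there is no inflation and only the missing description needs repair. Because the affected outcomes are behavioural and not primary, this should be fixed, but the trial's main conclusion does not depend on it.

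**What to change.** 1. State the row unit (day or season mean) and the full random-effects and variance structure for these outcomes.
2. If rows are days, add season-within-child and season-within-family random effects. Alternatively, use robust standard errors clustered on family, the unit that was randomized. Apply this to the ITT models, to the guideline models (at least 60 minutes MVPA, at most 120 minutes screen time) and to the weekday-only reruns.
3. Report valid days per child per season and the estimated child-by-season variance, so that readers can see how much the correction matters.

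**Cost:** a refit on existing data and wider intervals; some nominally significant findings may not survive.

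**Optional, for precision only:** model summer days adjusted for the child's spring mean, with child and family random effects, close to the diet design. Two cautions apply. Children without spring data would drop out unless the spring value is imputed, whereas the current likelihood approach keeps them. Randomization also preceded baseline assessment, so the spring measure may have been taken after allocation; the same caution applies to constraining the spring means to be equal between arms.

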Each spring (April/May) parents completed a brief survey via their smartphone to collect information about the child (e.g., biological sex, parent self-identified race/ethnicity), household income, parent highest education level obtained, household food insecurity status, and the use/receipt of any of the following services: Welfare, Temporary Assistance for Needy Families (TANF), Temporary Cash Assistance (TCA), Children's Health Insurance Program (CHIP), Medicaid, Supplemental Nutrition Assistance Program (SNAP), Women, Infants and Children (WIC), or Supplemental Security Income (SSI).

Summer Programming Exposure.

We recognized that children randomized to the control condition (i.e., summer as usual) could voluntarily elect to enroll in some type of summer programming. Based on national data, we anticipated approximately 20% of the children randomized to the control would attend some type of summer programming.¹⁴ Conversely, we recognized children randomized to receive free SDC could elect to not attend the free SDC or attend some other summer program offered. To account for differential exposure to summer programming in both the control and intervention groups, we collected information regarding summer programming attendance in three ways. First, at the beginning of summer (early June), parents completed a brief survey on their smartphone of the types of summer programming their child was anticipated to enroll in. Parents indicated the anticipated number of weeks enrolled in a program, the number of days per week the child was anticipated to attend, and whether the program was whole or half day. Second, on Friday of each week of the summer, parents received a text with a link to a brief survey about their child's attendance in a summer program for that week. Parents indicated if their child attended a summer program that week and, if yes, on what days of the week they attended, and for how long each day. Third, during a 14-day period in mid-July, parents were texted each evening at 9PM and asked to complete a daily time use record. Each record took ~7min to complete. Parents indicated the places/locations their child went during the day and the times they were there. Completed time use records for weekdays (the days when a child could attend a summer program) were used to estimate summer program exposure.

Statistical Power.

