Sample size calculations were based on the ability to detect a statistically significant group (intervention vs control) by time (before summer to end of summer) difference in the change in zBMI with a mixed-effects model with statistical power of 0.80 and an alpha of 0.05. Estimates from the largest and most recent studies¹⁵⁻¹⁷ conducted to date reported the average change in zBMI during the summer ranged from 0.04 to 0.09, and the average change in zBMI during the school year was -0.02. Accounting for the intraclass correlation at the school level¹⁸ and an anticipated attrition rate of 25%, the total number of children required to be enrolled at baseline was 420 to arrive at a final sample of 330 (165 per condition).

Statistical Analyses.

BMI. The primary analysis was intent-to-treat (ITT), defined as using all available data from children according to the original group they were randomized (free summer day camp or continue summer as usual) regardless of their attendance at a summer program. Analyses used mixed-effects models, accounting for the nesting of repeated measures within children, families (i.e., siblings), and schools. The treatment effect of interest was the group (intervention vs control) and time (pre summer vs post summer) interaction. Missing data on the primary outcome (zBMI) was accounted for using full information maximum likelihood estimation, allowing for all children's zBMI data to be used regardless of missing zBMI at either pre or post summer. Covariates included in

the model were the child's baseline zBMI, biological sex¹⁹ and age,²⁰ self-reported race/ethnicity,²¹ parent education,²² food insecurity status,²³ and poverty level.²⁴ Missing data on covariates were handled using multivariate multiple imputation of 100 datasets for both continuous and categorical covariates using STATA v18.0 multiple imputation commands. Secondary analyses examined the dose-response of summer program attendance including both the intervention and control groups. These models used each of the three summer program exposure metrics as continuous independent variables (standardized to the percentage of days attended during the week), to examine the impact of the amount of summer programming on changes in zBMI. The assumptions for all models were checked using plots of the estimated residuals, no violations were found.

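### As written, the covariate imputation for the movement-behaviour outcomes omits outcome, arm and attendance, so the non-randomised exposure models are under-adjusted to a degree that depends on unreported missingness

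*Combined protocol and SAP*

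**What the plan says.** Under Statistical Analyses, the paragraph on MVPA, screen time and sleep lists six adjustment variables: sex, age, race/ethnicity, parent education, food insecurity and poverty level. Missing values among them were filled in by "multivariate multiple imputation with the covariates serving as variables to inform the imputation of 100 datasets". Missing outcomes are treated separately: they "were accounted for using full information maximum likelihood estimation".

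The same section then describes secondary models that "examined the exposure to structured programming and included both the intervention and control groups". Exposure there is binary and set for each day: "any day where a child is reported on the TUR to have attended a structured setting outside the home". The covariates for these models are not listed again.

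The BMI paragraph says "Missing data on covariates were handled using multivariate multiple imputation of 100 datasets" and the diet paragraph says "Missing data for covariates was handled using multiple imputation of 100 datasets". Neither names the variables that informed the imputation. No section describes a complete-case analysis or an alternative imputation.

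**The concern.** An imputation model should contain every variable of the analysis it feeds, including the outcome and the exposure. If it does not, the imputed values carry no association with those variables beyond what the other covariates supply. The covariate's coefficient shrinks, and so does its power to remove confounding. Drawing 100 datasets reduces simulation noise but does not repair the model.

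This matters where adjustment has to replace randomisation. Under Summer Programming Exposure, control families "could voluntarily elect to enroll in some type of summer programming", and families offered the free camp could decline it. Attendance is therefore self-selected. Income, education and food insecurity plausibly bear on both attendance and child behaviour. If such covariates are incompletely imputed, the estimated effect of structured programming moves toward its unadjusted value.

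**Working it through.** The plan states no figure to reproduce, and the percent missing is not reported. The check is therefore of the mechanism, under assumed values.

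**By hand.** Let C be a confounder with a fraction p missing completely at random. Let β be its effect on the outcome and δ its association with attendance, both given the other covariates.

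- Leaving C out gives a bias of βδ.
- Covariates-only imputation scales both β and δ by about (1 − p), so adjustment removes about (1 − p)²βδ.
- The share of confounding that remains is about 1 − (1 − p)².

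This gives 1 − 0.95² = 10% at 5% missing, 1 − 0.90² = 19% at 10%, 1 − 0.80² = 36% at 20%, 1 − 0.70² = 51% at 30%, and 1 − 0.60² = 64% at 40%.

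**One value per child, by simulation.** The sample is 420 children, the enrolment target under Statistical Power. All other values are assumptions: an observed covariate correlated 0.3 with C; 1:1 arms; attendance depending on arm and on C (log-odds 0.6 per SD); outcome depending on C (0.3 SD per SD); true exposure effect 0; 600 replicates with 10 imputations each. Share left = (bias under covariates-only imputation − bias with complete data) / (unadjusted bias − bias with complete data).

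| Missing | Unadjusted | Complete data | Covariates only | With outcome, arm, attendance | Share left |
|---|---|---|---|---|---|
| 5% | 0.131 | −0.002 | 0.011 | −0.002 | 0.013/0.133 = 10% |
| 10% | 0.135 | 0.000 | 0.027 | 0.000 | 0.027/0.135 = 20% |
| 20% | 0.131 | −0.002 | 0.048 | −0.002 | 0.050/0.133 = 38% |
| 40% | 0.136 | 0.000 | 0.089 | 0.001 | 0.089/0.136 = 65% |

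Biases are in SD units, with Monte Carlo SE about 0.004. The shares agree with the hand formula. A second set of assumptions (400 children, continuous exposure, unadjusted bias 0.20) left 0.034/0.20 = 17%, 0.070/0.20 = 35% and 0.095/0.20 = 48% at 10%, 20% and 30% missing.

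**Day-level exposure with a child random intercept.** This is closer to the stated movement-behaviour models. With 10 days per child and an outcome intraclass correlation of 0.4 (both assumed), the share left was 18–19% at 10% missing and 51–52% at 30%. Adding arm and child-level means of attendance and outcome cut it to 0–1%. The share hardly changes, but it applies to a smaller bias, because much of the information comes from comparing days within a child, and a fixed child-level covariate cannot confound that comparison. In day-level models at 10% and 30% missing, the absolute bias was about 0.003 to 0.011 SD. Two other assumed set-ups bracket this. An unadjusted bias of 0.03 SD gives 0.03 × 0.19 = 0.006 and 0.03 × 0.51 = 0.015 SD. A model with 10 spring and 10 summer days gave at most 0.006 SD.

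**ITT contrast.** In the one-value-per-child set-up, the bias was at most 0.004 SD in absolute value under either imputation, with Monte Carlo SE about 0.004. That is no bias beyond simulation error.

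**The case against.** The sentence does not say that only the covariates were used. That is so, and a reader who infers that the other variables were deliberately excluded goes beyond the text. But the sentence does say what informed the imputation, and nothing elsewhere adds to that list, so a covariates-only model is its natural reading.

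Missingness may be slight. Under Randomization and Blinding, parents completed a screener on public assistance and parent education before allocation, which was stratified by public assistance, grade and gender. That limits gaps in education, sex and approximate age. Race/ethnicity, food insecurity and poverty level are the likelier places for gaps. This stands, and it could make the bias trivial.

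Three stronger readings are tempting:

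- That the exposure models rest entirely on these covariates. This is too strong for a day-level mixed model, which also draws on within-child comparisons.
- That the BMI and diet analyses contain the same error. Their sections name no imputation predictors, so the documents neither show it nor rule it out.
- That baseline zBMI was imputed without the post-summer value. The BMI section assigns missing zBMI at either time to full information maximum likelihood, so the documents do not support this.

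It is also true that unmeasured confounding of attendance remains under any imputation. That is a reason for caution about the exposure results, not for leaving an avoidable bias in them.

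**Conclusion.** The point holds for the exposure models of MVPA, sedentary time, sleep and screen time. The stated imputation rule, followed as written, leaves part of each incompletely observed covariate's confounding in place: about 20% at 10% missing and about 50% at 30% missing. In absolute terms this is small in a day-level random-intercept model, about 0.003 to 0.011 SD. With one value per child it is larger, for example 0.027 SD at 10% missing. The BMI dose-response models are nearer to that second case, but their imputation predictors are unstated.

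These sizes rest on assumed effect sizes and on data missing completely at random; the documents supply neither these values nor the percent missing. A reader might infer that the randomised comparisons are compromised. They are not: the ITT contrasts are essentially unaffected. The correction is worth making because it is standard and cheap, but it concerns secondary analyses only.

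**What to change.** For the movement-behaviour analyses, impute the covariates from a child-level model that contains:

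- the covariates themselves;
- child-level means of the spring and summer outcomes;
- arm (as a predictor; imputing separately within arm is optional);
- child-level attendance;
- study summer (2021, 2022 or 2023);
- the stratification factors.

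Then re-run the exposure models and report the percent missing for each covariate. State the imputation predictors for the BMI dose-response and diet as-treated analyses. If those also used covariates only, apply the same model there with their own outcomes. If the movement-behaviour imputation already contained these terms, correct the sentence that describes it; no re-run is then needed.

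No new data are required. The cost is some extra imputation work, because day-level and clustered data must first be summarised to child level, followed by a re-run of the secondary models.
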